4.5.10.2 Lumbar puncture (Research)

In the event that the lumbar drain fails and the patient opts against replacement of the lumbar drain on the floor, a lumbar puncture will be performed in the operating room on Day 8 for research purposes. This will be performed under general anesthesia. For the lumbar puncture, the patient will lie on their side, curled up with their knees at their chest, or sitting upright. Their lower back will be cleaned. A needle will be inserted through the numbed skin and into the space between the bones in their back. Up to 15 ml of cerebrospinal fluid (CSF) will be removed for research purposes, beyond what CSF is lost during usual performance of the procedure. After the fluid is collected, the patient will continue with surgical resection as indicated.

4.5.10.3 Bone Marrow Examination (Research)

For the bone marrow examination, aspirate and core biopsy may be collected according to conventional clinical technique from the hip of the patient. If the procedure is performed, it will be done by a clinical provider credentialed to perform this procedure, and is typically performed at the end of the research surgical procedure while the patient is under anesthesia. The decision to perform this examination is at the discretion of the primary investigator.

4.5.10.4 Stereotactic biopsy (Research)

Patients will undergo placement of a surgical head frame and will be registered into our neuronavigation system. A plan will be made on the neuronavigation for the location of the biopsy and the targets for placement of the microdialysis catheters. The biopsy and catheter sites as planned above will be prepped and draped in the usual sterile fashion. First, at the biopsy site, a small stab incision will be made, and the pneumatic drill will be used to make a small burr hole in the skull in the trajectory of the needle biopsy. The dura will be incised, the pial surface of the brain will be coagulated, and we will then open the pia. The needle will then be passed along the trajectory to the target using the neuronavigation system. Adequate biopsies will be taken to confirm the diagnosis of recurrence. This confirmation will be done by frozen section. There will be at least 4 samples taken, but there may be as many as 20, from different sites, if the diagnosis is hard to confirm. If a diagnosis of recurrent glioblastoma cannot be confirmed by the frozen section, the patient will not proceed with the rest of the study procedures. Once adequate tissue has been removed, the needle will be removed.

4.5.10.5 Microdialyis catheter placement (Research)

After the brain biopsy is performed confirming recurrent glioblastoma, the neuronavigation system will be utilized to plan a needle trajectory from two skull burr holes to the dialysis probe targets. The MD 71 catheter we will implant has one inlet and one outlet tube which is designed for sampling only. The surgeon's discretion will be used to pick solid, contrast-enhancing portions of the lesion that appear to best represent the most pathological portion of the tumor for microdialysis catheter placement. The surgeon's discretion will also be used to pick a second site that does not appear to be contrast-enhancing tumor for the peritumoral catheter. A stab incision on the scalp will be made at the site of each planned burr hole, one planned to go into the contrast enhancing tumor, and one into the peri-tumoral area, at least 10mm away from the contrast enhancing margin of the tumor, using neuronavigation system guidance as above. This will be done using the surgeon's discretion. We will assess the peritumoral catheter target using the following criteria:

- 1) A lack of contrast-enhancement as noted on the neuronavigation system
- 2) The closest adequate area to the tumor site, as assessed by the surgeon
- 3) Adequate brain tissue surrounding the placement site to allow the catheter to sit in the tissue undisturbed, as assessed by the surgeon
- 4) A safe path to the insertion site, as assessed by the surgeon

Once the dura and pial surface are pierced, as above, the catheter will be passed along the established trajectory into the brain tissue. A guide needle may be used to place the microdialysis catheter. The part of the catheter outside the skull will be tunneled under the skin to a second stab incision, where it will exit the scalp. The ends of the tubing connected to the cannulas will be sterilely sealed and secured. The scalp wound will be closed, and the head frame removed while anesthetized. Patients will be awakened from anesthesia and returned to the Intensive Care Unit for immediate postoperative care. The dialysis machines will be attached to each catheter in the ICU.

4.5.11 Computer-assisted Tomography (CT) Scan (Research)

This research study involves exposure to radiation from a CT scan of the head following biopsy/microdialysis catheter placement surgery to evaluate for the development of a blood clot and accurate placement of the microdialysis catheters.

4.5.13 CSF Sample retrieval (Research)

CSF will be taken daily while the subject is in the ICU and during the patient's inpatient stay. The lumbar drain will remain clamped until the time of sampling. At that time, the first 5ml will be drained off to allow the clearance of debris and sediment, and then up to 15ml of CSF will be collected for studies and stored at -80 degrees C. On Day 3, additional samples of up to 10ml of CSF will be drawn (total for Day 3 up to 25ml of CSF). Up to 5ml will be withdrawn before, and 6 hours +/- 2 hours after the completion of the nivolumab dose for pharmacokinetic analysis. In the event that the lumbar drain fails and is not replaced, CSF collection will cease until the lumbar puncture performed in the operating room on Day 8. Up to 15ml will be withdrawn in the operating room during the lumbar puncture.

4.5.14 Nivolumab (Research)

Nivolumab is a programmed death receptor-1 (PD-1) blocking antibody. Nivolumab monotherapy is approved in multiple countries, including the US and EU, for unresectable or metastatic melanoma, previously treated metastatic NSCLC, and previously treated advanced RCC; it is also approved for the treatment of cHL in the US. The FDA has recently approved Nivolumab for the treatment of patients with recurrent or metastatic squamous cell carcinoma of the head and neck (SCCHN) with disease progression on or after platinum-based therapy; and it was also approved for treatment of patients with locally advanced or metastatic urothelial carcinoma who have disease progression during or following platinum-containing chemotherapy or have disease

progression within 12 months of neoadjuvant or adjuvant treatment with a platinumcontaining chemotherapy. In addition, nivolumab has been approved for use in combination with ipilimumab for unresectable melanoma in multiple countries, including the US and EU. Nivolumab is being investigated both as monotherapy and in combination with chemotherapy, targeted therapies, and other immunotherapies. This drug will be provided as part of a drug-only sponsorship from Bristol-Myers Squibb. It will be given on study day 3 at a dose of 240mg given intravenously over 30 minutes. It will be given subsequently as an intravenous infusion over 30 minutes at a dosage of 240mg every 2 weeks together with BMS 986016, starting on Day 17 (+/- 2 days), as outlined in Section 1.6.4, above. It is produced by Bristol-Myers Squibb, New York, NY. The Investigator Brochure is listed as Appendix B. Please see section 4.5.19 for definition of duration of therapy.

4.5.15 Anti-LAG-3 antibody, BMS-986016 (Research)

BMS-986016 is a Lymphocyte Activation Gene-3 (LAG-3) blocking antibody which is undergoing study both as monotherapy and as combination therapy with Nivolumab for the treatment of advanced cancers. This drug will be provided as part of a drug only sponsorship from Bristol-Myers Squibb. It will be given beginning on study Day 17 (+/-2 days). It will be given as an intravenous infusion over 60 minutes at a dosage of 80mg every 2 weeks (+/- 2 days). It is produced by Bristol-Myers Squibb, New York, NY. The Investigator Brochure is listed as Appendix C. The patients will have BMS-986016 infusions every 2 weeks (+/- 2 days) with the Nivolumab until progression. Please see section 4.5.19, below, for discussion of duration of therapy.

4.5.16 Surgical Treatment and Post-operative care (Clinical Care)

After the conclusion of microdialysis monitoring, patients will undergo resection of their brain tumor as per protocol 03-N-0164. The beginning of this surgery will be noted as the start of Phase 2 of the study for safety monitoring purposes. The type of surgery that will be performed will be decided upon by the neurosurgeon and will be discussed with the patient before surgery.

When deemed necessary, as per standard clinical practice, a surgical procedure will be performed with intraoperative motor, sensory and speech mapping. The decision to perform a surgical procedure in an awake vs anesthetized manner will be determined based on standard clinical practice. Generally, awake surgery is employed in the case of language mapping, and in some cases for motor mapping, whereas intraoperative monitoring with anesthesia may be used for motor mapping. This surgery will be done in accordance with standard of care. The patients will receive a post-operative MRI, and will be watched in the Intensive Care Unit, as would be our typical practice, until the patient is stable for transfer to the Neurosurgical floor at the discretion of the treating physicians. When the patient is stable for discharge from the hospital, they will be discharged home or to a suitable rehabilitation facility, as indicated.

4.5.17 Repeat Bone Marrow Examination (Research)

For the bone marrow examination, aspirate and core biopsy may be collected according to conventional clinical technique from the hip of the patient. If the procedure is performed, it will be done by a clinical provider credentialed to perform this procedure, and typically is performed at the end of the research surgical procedure while the patient is under anesthesia.

4.5.18 Surgical specimens (Research and Clinical Care)

A portion of the brain tissue specimen will remain after the neuropathologist removes the amount that is required to make a pathologic diagnosis at both biopsy and resection. This remaining tissue will be used for research purposes, consistent with NIH guidelines under protocol 03-N-0164. Tissue obtained through this protocol will be evaluated for molecular, cellular, and genetic markers of tumor tissue and normal tissue. Specimens will be evaluated for inflammatory markers including cytokines, interleukins, TNF-a, T cells, microglia, and reactive astrocytes. Remaining tissue will be frozen and stored for use in brain research studies in the future either at NIH or at other institutions. We will obtain consent from patients to use their specimens in future studies and at other collaborating institutions.

Brain specimens stored in the tissue bank of the Surgical Neurology Branch, NINDS, will remain frozen until they are used. A biologist in the Surgical Neurology Branch will track brain specimens.

The banked and processed research specimens are coded and stored without personal identifiers. The specimens and data from this research will remain stored after completion of the protocol. Because research specimen testing does not affect the care of the patient, the patient will not be notified of the results of his/her research tests, nor will the results appear in the medical record or be given to the referring physician.

4.5.19 Follow-up (Research)

Upon discharge from the hospital, a summary letter will be sent to the patient's physician of record, describing the care rendered. Dosing of study medications will commence on Day 17 (+/- 2 days). Safety monitoring for infusions is discussed in section 8.2, below. Additionally, all patients will be seen in the Outpatient Neuroscience Clinic 2 weeks (+/- 1 week) after their surgery. This visit requirement is separate from the Day 17 (+/- 2 days) study visit. If appropriate, this post-operative care visit will be conducted in the day hospital, during the Day 17 (+/- 2 days) study visit. It may also occur on 7SW, if the patient remains admitted in the hospital, post-operatively. The patients will continue to receive Nivolumab, as above, at a dose of 240mg IV every two weeks and BMS-986016 antibody at a dose of 80mg IV every two weeks until progression. The first dose of both study medications will begin on study Day 17 (+/- 2 days). Details of the infusion can be found in section 1.6.4. Between study visits, no specific precautions are needed. Patients will be reminded to call us with any clinical concerns regarding potential adverse events, including, but not limited to GI concerns, neurological compromise, signs of adrenal

insufficiency, skin lesions, hypophisitis, respiratory concerns, cardiovascular compromise, renal insufficiency or liver failure. Detailed safety monitoring procedures are outlined in section 8, below. Section 8.6 contains the list of toxicities which will prompt automatic discontinuation of the study drugs. Additionally, we will follow the I-O treatment algorithm for Nivolumab in Appendix B, below. Steroids will be used for symptomatic management as needed, per the discretion of the treating physician. Steroid use will not be a criterion for removal from the study.

Prior to documenting removal from protocol therapy, effort must be made to have all subjects complete a safety visit approximately 30 days following the last dose of study therapy.

In the absence of treatment delays due to adverse event(s), treatment may continue as specified in the above treatment modality sections or until one of the following criteria from section 8.6, below, occurs.

Subjects initially meeting radiologic criteria for disease progression may continue receiving study medication until confirmation of progression. Progression will be defined by Response Assessment in Neuro-Oncology Criteria (RANO) criteria, as it has been adopted for immunotherapy trials[38]. The initial radiological suspicion of progression will be raised when:

 $- \ge 25\%$ \uparrow sum of biperpendicular diameters of enhancing disease (new lesions will be added to the sum of the diameter of enhancing disease during the treatment period and will not automatically be assumed to be progression).

This continuation of therapy can continue for a total of 12 weeks with MRIs performed every 4 weeks, as per protocol. iRANO criteria has suggested that this treatment extension only be implemented during the first 6 months of therapy, however there is not yet enough data about treatment of recurrent glioblastoma patients with checkpoint inhibition to be sure of the time course of pseudoprogression. As such, this additional observation period will be implemented at any time while patients are on study medications. Patients will only be eligible to continue therapy in the face of MRI evidence of potential progression if the patient is believed to be demonstrating clinical benefit as deemed by the investigator, the patient is tolerating the study medications and the patient has not significantly declined, neurologically. Of note, if the patient's decline reverses with corticosteroids or surgical sampling of the patient's mass demonstrates treatment effect only, the patient may continue on therapy or resume therapy.

Subjects with confirmed radiologic progression (approximately 12 weeks after initially assessed progression) will discontinue study medication and enter the survival follow up phase of the study. If progression is confirmed, then the date of disease progression will be the first date the subject met the criteria for progression.

To determine clinical progression, subjects with neurological decline will receive a clinical MRI to evaluate for progression by imaging (standard of care).

During Phase 2, in any patient with significant neurologic decline where disease progression cannot be differentiated from pseudoprogression, and/or in n those cases in which radiologic progression cannot be differentiated from pseudoprogression and it is the investigator's opinion that a surgical biopsy or resection to obtain tumor tissue for histopathology is in the subject's best interests, a surgical resection may be performed following consultation with the medical monitor and outside consultant neurosurgeon. If tumor pathology confirms progression, then the subject will be discontinued from study medication per protocol discontinuation criteria and the date of progression will be the day that it was first suspected. If the patient's decline reverses with corticosteroids and/or tumor pathology reveals treatment-related changes and does not confirm disease progression, we will discuss resumption of therapy with our Safety Monitoring Committee (for patients enrolled at NIH) and the Data and Safety Monitoring Board (for patients enrolled at the Emory Site). The subject will then continue all on-treatment tumor assessments as per the treatment schedule.

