4.7 End of participation

Active participation in this protocol and treatment with BMS-986016 and nivolumab will end upon:

- clinical progression (neurological decline followed by confirmation of progression by imaging or pathological diagnosis) or
- confirmed radiological progression and investigator determination that the patient is no longer benefiting from treatment with the study treatment or
- meeting any other "Criteria for individual subject withdrawal" as listed in section 8.6

After this point, participants will be considered on survival follow-up until death. For subjects removed for clinical or radiological progression as described above, we will perform a follow-up assessment at the next scheduled imaging visit and no less than 4 weeks after the prior assessment of disease progression.

Survival Follow-up Phase

Participants who have discontinued study medication will enter the survival follow-up phase of the study after their final follow-up assessment. Participants enrolled at the NIH Clinical Center site will continue to be enrolled in protocol 03-N-0164 and data on subject progress will be shared with this protocol (NIH medical/research records). For those who decide to pursue care elsewhere and not through protocol 03-N-0164, we will perform phone calls approximately monthly to check on the status of the individual until death. We will attempt to gather Karnofsky Performance Status Rating, ongoing treatment information, follow-up any potential side effects from this study treatment, and vital status (alive/deceased).

During this phase, patients may transfer their care to an outside physician, or they may choose to enroll in further studies at the NIH Clinical Center under the care of the investigators of this protocol. If they chose to pursue their treatment outside of the NIH, all the medical care records will be transferred to the outside physician, with the subject's permission. Further consultation at the NIH under another NIH protocol will be possible by referral.

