9.2 Exploratory outcome measures

Exploratory outcome measures and include:

- 1. The change in interferon gamma expression from before, during and after Nivolumab treatment in the brain microenvironment, cerebral spinal fluid and the blood.
- 2. The difference between the IHC staining for CD3, CD4, CD8, CD20, CD45RO, CD57, CD68, FOXP3, Granzyme B, LAG3, PD-1, CD14, CD33, CD163, and CD206 before and after Nivolumab therapy. These markers will be evaluated as density of cells, defined as the number of positive cells per mm². PD-L1 expression will be evaluated in tumor cells using H-score, which includes the percentage of positive cells showing membrane staining pattern (0–100) multiplied by the intensity of the staining (0 to 3+), with a total score ranging from 0 to 300. The final score for each marker will be expressed as the average score of the areas analyzed within the tumor region (tumor center).
- 3. Progression free survival and overall survival of recurrent glioblastoma patients after treatment. Progression free survival is defined as the time length from the first dose of study drug with recurrence to progression as defined by iRANO criteria, and the overall survival is defined as the time length from the first dose of study drug to death. If a lesion is 25% larger but there remains a question as to disease progression or pseudoprogression due to treatment, the patient can remain on treatment until this can be defined. If true progression occurred earlier, the earlier date will be used for censorship. If patient is lost to follow-up prior to documented progression or death, patient will be censored as of the date of the last adequate evaluation (MRI and exam). If patient dies prior to documentation of progression, progression will be defined as the date of death, if patient has been attending regularly scheduled follow-ups.
- 4. The difference in progression free survival and overall survival between patients who have an interferon gamma response versus those that do not have one.

5. The difference in the immune cells and secreted factors of the tumor environment as compared to the immune cells and secreted factors of the cerebral spinal fluid, blood and potential bone marrow in response to this treatment

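### Progression is back-dated to first suspicion only if later confirmed, so a patient who dies before confirmation gets a longer PFS than one with the same scan who survives to it, and a patient lost before confirmation loses the event

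*Combined protocol and SAP*

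**What the plan says.** The PFS rules are spread over several sections of the combined protocol and SAP.

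- **Origin (9.2, item 3):** "Progression free survival is defined as the time length from the first dose of study drug".
- **Confirmed by imaging (4.5.19):** "If progression is confirmed, then the date of disease progression will be the first date the subject met the criteria for progression". The timing is given in the sentence before: "Subjects with confirmed radiologic progression (approximately 12 weeks after initially assessed progression) will discontinue study medication".
- **Confirmed by pathology (4.5.19):** "the date of progression will be the day that it was first suspected".
- **Death (9.2, item 3, and 4.5.20):** "If patient dies prior to documentation of progression, progression will be defined as the date of death", on condition that the patient was attending scheduled follow-ups.
- **Loss to follow-up (9.2, item 3, and 4.5.20):** before documented progression or death, the patient is censored at the last adequate MRI and exam.
- **Treatment through the window (4.5.19):** "This continuation of therapy can continue for a total of 12 weeks with MRIs performed every 4 weeks, as per protocol". Among the conditions is that "the patient has not significantly declined, neurologically".
- **After removal for progression (4.7 and 8.6):** a follow-up assessment takes place "at the next scheduled imaging visit and no less than 4 weeks after the prior assessment of disease progression".

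Item 3 of 9.2 also says that an earlier date is used for *censorship* where true progression occurred earlier. PFS is exploratory, estimated by Kaplan-Meier (10.1), and described by interferon gamma response (9.2, item 4).

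**The concern.** Back-dating depends on an event in the future. A first qualifying MRI becomes the progression date only if the patient remains under observation long enough for imaging or pathology to confirm it. If death comes first, the scan has no stated role and the event moves to the date of death. If the patient is lost first, the scan has no stated role as an event and the patient is censored. The same MRI therefore yields different PFS records depending on what happens afterwards.

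The affected patients are unlikely to be a random subset, since those who die or drop out within weeks of a suspicious scan tend to be doing badly. With a target of 10 completed patients (3.1), a few such cases can move the PFS estimate. They can also distort the responder versus non-responder description if they fall unevenly between the two groups.

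**Working it through.** The documents give no PFS median, event count or power, so there is no figure to reproduce. The check applies the stated dating rules to patients with the same qualifying scan.

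**Inputs from the documents.** First dose on Day 3 (4.5.14); MRI on Day 17 and every 4 weeks after (25.0, Study Calendar); imaging confirmation about 12 weeks = 84 days after suspicion (4.5.19).

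**Assumed.** All patients first meet the 25% criterion on the Day 73 scan, and it is true progression.

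**Formula.** PFS in weeks = (day of event or censoring − 3) / 7. Scheduled scans on Days 17, 45, 73, 101, 129 and 157 fall at weeks 2, 6, 10, 14, 18 and 22. Suspicion is at (73 − 3)/7 = 10.0 weeks; imaging confirmation is at (73 + 84 − 3)/7 = 22.0 weeks.

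| What happens after the Day 73 scan | Recorded PFS (weeks) | Status | Excess over 10.0 |
|---|---|---|---|
| Confirmed at week 22 | 10.0 | event | 0 |
| Dies Day 87, unconfirmed | 12.0 | event | 2 |
| Dies Day 101, unconfirmed | 14.0 | event | 4 |
| Dies Day 115, unconfirmed | 16.0 | event | 6 |
| Dies Day 129, unconfirmed | 18.0 | event | 8 |
| Dies Day 156, unconfirmed | 21.9 | event | 11.9 |
| Lost, last MRI Day 73 | 10.0 | censored | 0, event lost |
| Lost, last MRI Day 101 | 14.0 | censored | 4, event lost |
| Lost, last MRI Day 129 | 18.0 | censored | 8, event lost |

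For deaths, the excess is the time from suspicion to death. If the first study dose were instead taken as Day 17, every time would fall by 2 weeks and every difference would stay the same.

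**Direction on a Kaplan-Meier curve.** This uses ten assumed patients (not trial data), with first suspicion at weeks 2, 6, 6, 6, 10, 10, 10, 14, 18 and 22. The median is the first time the estimate is at or below 0.5.

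- All dated at first suspicion: the curve is 0.6 at week 6 and 0.3 at week 10, so the median is 10 weeks.
- Three of them (two at week 6, one at week 10) die unconfirmed 6 weeks after suspicion: 0.6 at week 10 and 0.4 at week 12, so the median is 12 weeks.
- The same three censored at the qualifying scan: 0.533 at week 10 and 0.356 at week 14, so the median is 14 weeks.
- The same three censored one scan later: 0.6 at week 10 and 0.45 at week 14, so the median is 14 weeks.

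**With the dating proposed below.** Every patient in the table has PFS 10.0 weeks with an event, and the gap is 0.

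**The case against.** The strongest reply is that 9.2 already covers the case. Its earlier-date sentence follows directly on the discussion of a lesion that has grown by 25%, and is not tied to a 12-week scan. If it is applied to these deaths, or if *documentation* means the first qualifying scan, the gap closes. But the sentence requires a finding of true progression, which an unconfirmed patient lacks, and it speaks of censorship rather than an event date. *Documentation* is nowhere defined, and 4.5.19 treats the first qualifying scan as suspicion only. Two analysts could date the same patient differently.

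A second reply is that declining patients need not wait 12 weeks. Section 4.5.19 sends them for an MRI, 4.7 accepts imaging or pathology as confirmation of clinical progression, and pathology back-dates to first suspicion. This stands, and it limits how many patients are affected. A reader might infer that the sickest patients can never be confirmed, so that their overstatement has no limit and PFS becomes overall survival. The documents do not support that. Besides these routes, 4.7 has progress data shared from the companion NIH protocol for participants who stay in it.

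A reader might also infer that stopping imaging earns a longer PFS. It does not: such a patient is censored, at the same time or 4 to 8 weeks later in the cases above, and the harm is the lost event.

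Third, the plan relies on published immunotherapy response criteria, which might date unconfirmed progression. That cannot be checked from the documents, and the protocol's own sentences would still need reconciling with them.

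Finally, counting unrefuted suspicion as progression sits uneasily with the plan's concern about pseudoprogression. That is a fair cost, and a reason for a sensitivity analysis.

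**Conclusion.** The concern holds for deaths before confirmation, and in a different form for losses before confirmation. On the plain reading, a death in the window adds the time from suspicion to death to PFS, up to about 12 weeks. A loss in the window removes an event, and the censoring is probably informative. Both raise the PFS curve relative to dating every true progression at its first qualifying scan.

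This rests on the scan being true progression, on *documentation* meaning confirmation, and on no earlier confirmation by decline-triggered MRI or pathology. The number of patients affected is unknown; the patient timelines and the ten-patient set show direction only.

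The reach is limited to exploratory PFS in about 10 patients and the descriptive comparison by interferon gamma response. Distortion of that comparison is possible, not shown. No primary outcome is affected. A reader might also set 12 weeks against the 31-week median survival in section 1.2. That figure is overall survival after a different treatment and does not measure the size of this problem. The wording should be corrected before PFS is analysed.

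**What to change.** For endpoint dating only, in 9.2 item 3, 4.5.19 and 4.5.20:

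- State that a qualifying MRI (at least 25% growth) not refuted by later imaging or pathology is a PFS event dated at that MRI, including when death, loss to follow-up or new anti-tumor treatment comes before confirmation.
- Define *documentation* of progression to match.
- In 9.2 item 3, replace *censorship* with *event date* in the earlier-date sentence.
- Say whether the follow-up assessment at least 4 weeks later (4.7, 8.6) counts as confirmation for PFS.
- Report a sensitivity analysis using the current dating: date of death, or censoring at the last adequate evaluation.

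The cost is wording and one extra analysis, with no new scans. Some PFS times become shorter, and pseudoprogression that is never re-imaged will count as an event; the sensitivity analysis shows how much that matters. No change to the rules for continuing treatment is proposed.
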